7.1.2. Clinical laboratory parameters and other abnormal assessments qualifying as SAEs

In absence of diagnosis, abnormal laboratory findings (e.g., clinical chemistry, haematology, urinalysis) or other abnormal assessments that are judged by the

investigator to be clinically significant will be recorded as SAEs if they meet the definition of an SAE (refer to Section 7.1.1). Clinically significant abnormal laboratory findings or other abnormal assessments that are present at baseline and significantly worsen following the start of the study will also be reported as SAEs. However, clinically significant abnormal laboratory findings or other abnormal assessments that are associated with the disease being studied, unless judged by the investigator as more severe than expected for the subject's condition, or that are present or detected at the start of the study and do not worsen, will not be reported as SAEs.

The investigator will exercise his or her medical and scientific judgement in deciding whether an abnormal laboratory finding or other abnormal assessment is clinically significant.

7.2. Detecting and recording SAEs

7.2.1. Time periods for detecting and recording SAEs

SAEs related to study participation will be collected and recorded from the time of the first study visit until the subject is discharged from the study.

In order to fulfil international reporting obligations, SAEs that are related to study participation (i.e., protocol-mandated procedures, invasive tests, a change from existing therapy) will be collected and recorded from the time when the subject parent(s)/ LAR(s) have consented their child's/children's participation in the study until she/he is discharged from the study.

7.2.2. Evaluation of SAEs

7.2.2.1. Active questioning to detect SAEs

Each subject's parent(s)/LAR(s) will be instructed to contact the investigator immediately should the subject manifest any signs and symptoms (s) they perceive as serious.

All SAEs either observed by the investigator or his/ her staff or reported by the subject's parent(s)/LAR(s) spontaneously or in response to a direct question will be evaluated by the investigator. The nature of each event, date and time of onset, outcome, intensity and possible relationship to the study procedures should be established.

When an SAE occurs, it is the responsibility of the investigator to review all documentation (e.g., hospital progress notes, laboratory and diagnostics reports) relative to the event. The investigator will then record all relevant information regarding the SAE in the eCRF. The investigator is not allowed to send photocopies of the subject's medical records to GSK Biologicals instead of appropriately completing the eCRF. However, there may be instances when copies of medical records for certain cases are requested by GSK Biologicals. In this instance, all subject identifiers will be blinded on the copies of the medical records prior to submission to GSK Biologicals.

The investigator will attempt to establish a diagnosis pertaining to the event based on signs, symptoms, and/ or other clinical information. In such cases, the diagnosis should be documented as the SAE and not the individual signs/symptoms.

7.2.2.2. Assessment of causality

The investigator should assess the causality of each SAE. The investigator will use clinical judgement to determine the relationship between the SAEs and study participation. Alternative causes, such as natural history of the underlying diseases, other concomitant therapy and other risk factors will be considered and investigated.

There may be situations when a SAE has occurred and the investigator has minimal information to include in the initial report to GSK Biologicals. However it is very important that the investigator always makes an assessment of causality for every event prior to submission of the SAE report to GSK Biologicals. The investigator may change his/her opinion of causality in light of follow-up information and update the SAE information accordingly.

If an event meets the criteria to be considered as 'serious' (see section 7.1.1), additional examinations/tests will be performed by the investigator in order to determine ALL possibly contributing factors to each SAE.

Possibly contributing factors include:

- Medical history.
- Concomitant medication.
- Protocol required procedure.
- Other procedure not required by the protocol.
- Other cause (specify).

7.2.2.3. Assessment of outcomes

The investigator will assess the outcome of all SAEs recorded during the study as:

- Recovered/resolved.
- Recovering/resolving.
- Not recovered/not resolved.
- Recovered with sequelae/resolved with sequelae.
- Fatal (SAEs only).

7.3. Reporting of SAEs

All SAEs occurring up to 30 days after the study procedure and considered related to study participation must be recorded on the SAE form, irrespective of intensity.

7.3.1. Prompt reporting of SAEs related to study participation

SAEs that occur in the time period defined in Section 7.2.1 will be reported promptly to GSK within the timeframes described in Table 11 once the investigator determines that the event meets the protocol definition of an SAE.

Table 11 Timeframes for submitting SAEs related to study participation

Type of event		Initial reports	Follow-up of relevant information on a previous report		
	Timeframe	Documents	Timeframe	Documents	
SAEs related to study participation	24 hours*	electronic expedited adverse event report	24 hours*	electronic expedited adverse event report	

* Timeframe allowed after receipt or awareness of the information.

7.3.3. Completion and transmission of SAE reports related to study participation to GSK

Once an investigator becomes aware that an SAE has occurred in a study subject, the investigator (or designee) must complete the information in the electronic SAE report WITHIN 24 HOURS. The SAE report will always be completed as thoroughly as possible with all available details of the event. Even if the investigator does not have all information regarding an SAE, the report should still be completed within 24 hours. Once additional information is received, the report should be updated WITHIN 24 HOURS.

The investigator will always provide an assessment of causality at the time of the initial report.

7.3.3.1. Back-up system in case the electronic SAE reporting system does not work

If the electronic SAE reporting system does not work, the investigator (or designee) must complete, then date and sign a paper SAE report and fax it to the GSK Biologicals Clinical Safety and Pharmacovigilance department within 24 hours.

This back-up system should only be used if the electronic SAE reporting system is not working and NOT if the system is slow. As soon as the electronic SAE reporting system is working again, the investigator (or designee) must complete the electronic SAE report

within 24 hours. The final valid information for regulatory reporting will be the information reported through the electronic SAE reporting system.

7.3.4. Updating of SAE after freezing of the subject's eCRF

When additional SAE information is received after freezing of the subject's eCRF, new or updated information should be recorded on a paper report, with all changes signed and dated by the investigator. The updated report should be faxed to the GSK Biologicals Clinical Safety and Pharmacovigilance department or to the Study Contact for Reporting SAEs (see the Sponsor Information) within the designated reporting time frames specified in Table 11.

7.3.5. Regulatory reporting requirements for SAEs

The investigator will promptly report all SAEs to GSK Biologicals in accordance with the procedures detailed in Section 7.3.1. GSK Biologicals has a legal responsibility to promptly notify, as appropriate, both the local regulatory authority and other regulatory agencies about the safety of a product under epidemiological investigation. Prompt notification of SAEs by the investigator to the Study Contact for Reporting SAEs is essential so that legal obligations and ethical responsibilities towards the safety of other subjects are met.

7.4. Follow-up of SAEs

7.4.1. Follow-up of SAEs

7.4.1.1. Follow-up during the study

After the initial SAE report, the investigator is required to proactively follow each subject and provide further relevant information on the subject's condition to GSK Biologicals (within 24 hours for SAEs, refer to Table 11).

All SAEs documented at a previous visit/ contact and recorded as not recovered/ not resolved or recovering/ resolving will be reviewed at subsequent visits/ contacts until the end of the study.

7.4.1.2. Follow-up after the subject is discharged from the study

The investigator will follow-up subjects:

• With SAEs until the event has resolved, subsided, stabilized, disappeared, or until the event is otherwise explained, or the subject is lost to follow-up.

If the investigator receives additional relevant information on a previously reported SAE, he/ she will provide this information to GSK Biologicals using a paper SAE report.

GSK Biologicals may request that the investigator performs or arranges for the conduct of additional clinical examinations/ tests and/ or evaluations to elucidate as fully as possible the nature and/ or causality of the SAE. The investigator is obliged to assist. If a subject dies during participation in the study or during a recognized follow-up period, GSK Biologicals will be provided with any available post-mortem findings, including histopathology.

8. SUBJECT COMPLETION AND WITHDRAWAL (AMENDED 15-DEC-2017)

8.1. Subject completion

A subject who is available for the concluding contact foreseen in the protocol *for the primary study* is considered to have completed the *primary* study.

A subject who is available for the concluding contact foreseen in the protocol for the extension study is considered to have completed the extension study.

8.2. Subject withdrawal

Subjects who are withdrawn *from the study* because of *study procedure related* SAEs must be clearly distinguished from subjects who are withdrawn for other reasons. *Investigators* will follow subjects who are withdrawn *from the study* as *the* result of a *study procedure related* SAE until resolution of the event (see Section 7.4.1.2).

Withdrawals will not be replaced.

From an analysis perspective, a 'withdrawal' from the study refers to any subject who was not available for the concluding contact foreseen in the protocol.

All data collected until the date of withdrawal/last contact of the subject will be used for the analysis.

A subject is considered a 'withdrawal' from the study when no study procedure has occurred, no follow-up has been performed and no further information has been collected for this subject from the date of withdrawal/last contact.

Information relative to the withdrawal will be documented in the eCRF. The investigator will document whether the decision to withdraw a subject from the study was made by the, by the subject's parent(s) or LAR(s), or by the investigator, as well as which of the following possible reasons was responsible for withdrawal:

- SAE.
- Non-serious AE.
- Protocol violation (specify).
- Consent withdrawal, not due to an AE*.

- Moved from the study area.
- Lost to follow-up**.
- Other (specify).

*In case a subject is withdrawn from the study because the subject's parent(s)/ LAR(s) has/have withdrawn consent, the investigator will document the reason for withdrawal of consent, if specified by the subject's parent(s)/LAR(s), in the CRF.

**Details concerning the definition of "lost to follow up" are presented in the SPM.

9. STATISTICAL METHODS (AMENDED 15-DEC-2017)

9.1. Endpoints for the *Primary Study* (first 2 years)

9.1.1. Co-Primary endpoints

- Occurrence of RSV as confirmed by RT-qPCR.
- Occurrence of different types of healthcare utilization*.

* Healthcare utilization includes primary, secondary and tertiary care settings such as self-care with OTC drugs, GP visits, ER visits, hospital visits, etc.

- Occurrence of LRTI/severe LRTI as classified by the LRTI case definition and severity scale.
- Occurrence of LRTI/severe LRTI as classified by the existing comparator LRTI case definition by WHO and by Nokes et al.

9.1.2. Secondary endpoints

- Levels of RSV neutralizing antibodies in the cord blood samples collected at birth.
- Levels of RSV neutralizing antibodies in the blood samples collected at 2, 4, 6, 12, 18 and 24 months.
- Occurrence of LRTI/severe LRTI cases as classified by the LRTI case definition and severity scale, in the subgroups of subjects recruited from Months 1-6 and 13-18.

9.1.3. Tertiary endpoints

- Occurrence of RSV and other respiratory viruses as confirmed by xTAG[™] RVP Fast assay:
 - Parainfluenza virus type 1, 2, 3, and 4
 - Human Metapneumovirus
 - Rhinovirus
 - Adenovirus

- Bocavirus
- Coronavirus 229E, OC43, NL63, HKU1
- RSV
- Influenza A, including subtypes H1 and H3
- Influenza B
- RSV viral load as determined by RSV RT-qPCR.
- Occurrence of any symptom identified in cases of potential LRTI.
- Cord-blood sample collection variables including collection and storage times and temperatures.
- Occurrence of potential risk factors including complications at birth, family history of respiratory disease, living environment and household composition, breastfeeding, passive smoking and day-care attendance.

9.2. Endpoints for the Extension Study

9.2.1. Primary: none

9.2.2. Secondary:

- Occurrence of medically attended wheeze
- Occurrence of wheeze or asthma requiring hospital admission.
- *Use of* prescription medications for wheeze or asthma.

9.2.3. Tertiary

- Number of children with asthma (case definition 1) at age 2, 3, 4, 5, and 6 years of age
- Number of children with asthma (case definition 2) at age 2, 3, 4, 5 and 6 years of age.
- Number of children with asthma (case definition 3) at 3, 4, 5 and 6 years of age.
- Number of children with recurrent wheeze.

9.3. Determination of sample size

Different RSV-associated LRTI hospitalization rates have been reported in industrialized countries. We observe incidence rates between 16.9 and 44.1 per 1000 children-years in the age group of infants below 6 months of age, between 5.1 and 14.2 per 1000 children-years in the age group of infants between 6-11 months and between 0.4 and 3.7 per 1000 children-years in the age group of children between 12-23 months [Table 12]. These rates are similar to the ones measured in several studies conducted in developing countries [Nair, 2010].

Source	Region	0-5 months	6-11 months	12-23 months
[Hall, 2009]	USA	16.9	5.1	2.7
[Holman, 2004]	USA	41.9	12.8	-
[lwane, 2004]	NY/ Tennessee	18.5	7.4	0.4
[Boyce, 2000]	Tennessee	44.1	15.0	3.7
[Despande, 2003]	UK	36.0	11.3	-
[Vicente, 2003]	Spain	36.8	14.2	-

Table 12RSV-associated LRTI hospitalization rates in industrialized countries
(per 1000 children-years)

USA = United States of America

UK = United Kingdom

Table 13 shows the exact 95% confidence interval (CI) (Poisson exact distribution and normal approximation of the Poisson distribution accounting for a design effect of 4.18) for a range of expected incidence rates of RSV that we can reasonably estimate between 10 and 50 per 1000 children-years in the first year of birth. With an overall sample size of about 320 evaluable subjects by country during the first year of enrollment and with a follow-up period of 1 year after the last subject is recruited, the CI for an expected RSV-associated LRTI hospitalization rate of 20 cases per 1000 children-years is respectively [6.9; 40.8] for the exact Poisson distribution and [0; 51.7] for the normal approximation with design effect of 4.18.

Table 13Precision for expected RSV-associated LRTI hospitalization rate
during the first year of life (per 1000 children-years)

	Number of children-years	Number of cases	RSV-associated LRTI rate (per 1000 children-years)	95% CI Poisson Exact	95% CI Normal approx. with DE			
First year of enrollment (analysis will be performed 1 year after the last subject is recruited)								
Country/region level	320	3	10	[1.9; 27.4]	[0; 32.4]			
	320	6	20	[6.9; 40.8]	[0; 51.7]			
	320	10	30	[13.9; 55.4]	[0; 68.8]			
	320	13	40	[20.5; 67.5]	[0; 84.8]			
	320	16	50	[28.6; 81.2]	[0; 100.1]			
Overall	1280	13	10	[5.1; 16.9]	[0; 21.2]			
	1280	26	20	[13.0; 29.3]	[4.2; 35.8]			
	1280	38	30	[21.0; 40.7]	[10.6; 49.4]			
	1280	51	40	[29.7; 52.4]	[17.6; 62.4]			
	1280	64	50	[38.5; 63.8]	[25.0; 75.0]			
Second year of enrollment (analysis will be performed 1 year after the last subject is recruited)								
Country/region level	160	2	10	[0.7; 40.1]	[0; 41.7]			
	160	3	20	[3.9; 54.8]	[0; 64.8]			
	160	5	30	[8.4; 68.5]	[0; 84.9]			
	160	6	40	[13.8; 81.6]	[0; 103.4]			
	160	8	50	[21.6; 98.5]	[0; 120.8]			
Overall	640	6	10	[3.4; 20.4]	[0; 25.8]			
	640	13	20	[10.2; 33.7]	[0; 42.4]			
	640	19	30	[17.9; 46.4]	[2.6; 57.4]			
	640	26	40	[25.9; 58.6]	[8.3; 71.7]			
	640	32	50	[34.2; 70.6]	[14.6; 85.4]			

CI = Confidence Interval; RSV = Respiratory Syncytial Virus; LRTI = Lower Respiratory Tract Infection; DE = Design Effect

The design effect measures the increase in the standard error of the estimate due to the sampling design. The following formula will be used to estimate the design effect in the simulation [Bennett, 1991]:

$$DE = \frac{s^2_{cluster \ sample}}{s^2_{simple \ random \ sample}}$$

With

$$s_{cluster \, SAMPLE}^{2} = (c/\sum_{i} x_{i})^{2} (\sum_{i} y_{i}^{2} - 2p \sum_{i} x_{i} y_{i} + p^{2} \sum_{i} x_{i}^{2}) / [c(c-1)]$$

$$s^2_{SIMPLE RANDOM SAMPLE} = p(1-p)/n$$
Where, 'c' is the number of clusters, 'x_i', and 'y_i' are number of children-years and number of cases, respectively in the 'ith' cluster, 'n' is the total number of children-years and 'p' is the overall proportion ' $\sum y_i/\sum x_i$ '.

The intra-cluster correlation ' ρ ' may then be estimated as:

$$\rho = (DE - 1)/[(\sum x_i/c) - 1]$$

Each simulation consists of creating 'c' clusters whose size and incidence vary around a given value. Then the above formula was applied to estimate the design effect in the simulation. Table 14 shows the median result of 1000 simulations (with 5th and 95th percentile). The design effect [Bennett, 1991] can be estimated as following once the intra-cluster correlation value is known or can be assumed:

$$DE = 1 + (b - 1) \rho$$

Where, ρ is the intra-cluster correlation and b is the average number of subjects sampled per cluster. According to the results of simulations, we could assume that the intra-cluster correlation of 0.02 (See Table 14 below) and considering 12 clusters of 160 subjects, we expect that the design effect will take a value of 4.18.

Table 14	Design effect calculated from 1000 simulations and for different
	hypothesis

Hypothesis of the	Results of 1000 simulations				
simulation (Number of clusters; Overall number of children- years; incidence)	Number of children-years by cluster (P5; Median; P95)	Proportion of cases by cluster (P5; Median; P95)	DE : Design Effect (P5; Median; P95)	ρ : intra-cluster correlation (P5; Median; P95)	
9; 2400; 0.03	136; 266; 401	0; 0.028; 0.086	2.51; 6.46; 13.67	0.006; 0.021; 0.047	
12; 2400; 0.03	100; 201; 300	0; 0.027; 0.087	2.57; 5.13; 9.49	0.008; 0.021; 0.042	
15; 2400; 0.03	81; 160; 239	0; 0.027; 0.088	2.29; 4.34; 7.74	0.008; 0.021; 0.042	
18; 2400; 0.03	68; 133; 199	0; 0.026; 0.091	2.08; 3.89; 6.69	0.009; 0.022; 0.043	

P = Percentile

Few active studies reported the overall RSV-associated LRTI incidence rates (with or without hospitalization). According to the results observed in a birth cohort conducted in Kenya [Nokes, 2008] we expect that the RSV-associated LRTI rate will be 8 times greater than the hospitalization rate.

As the subjects may dropout from the study due to a variety of reasons, e.g. migration from the study area, the sample size has been increased to accommodate the same. Assuming a drop-out rate of about 20% during the course of follow-up approximately 400 subjects by country/region and 2400 subjects overall will need to be recruited.

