11.1.2. Exact confidence intervals (CIs)

The exact confidence interval within a group for an incidence rate (per 100 person-years):

To estimate the confidence limit of the incidence rate, the exact Poisson confidence limit will be used [Clopper, 1990]:

If *n* is the number of subjects presenting a given characteristic among these *Ny* subjects per year, the true incidence rate can be estimated by (n/Ny)*100. Its exact (1 -)% confidence interval is obtained from:

CINV(/2, 2*n)/2/Ny*100 as the lower boundary

and

CINV((1- /2),2(n+1))/2/Ny*100* as the upper boundary.

where *CINV(probability, degrees of freedom)* returns the inverse of the chi-squared probability distribution and is the type I error rate.

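### Eight of the 20 exact Poisson intervals in protocol Table 13 are not the exact interval for the case count printed beside them; the error is small and needs only a minor correction

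*Protocol*

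**What the plan says.** Section 9.3 of the protocol supports the sample size by precision, not power. It states that "Table 13 shows the exact 95% confidence interval (CI) (Poisson exact distribution" and, beside it, a normal approximation with a design effect. The rates considered are "between 10 and 50 per 1000 children-years in the first year of birth". Table 13 has four blocks of five rates: country level and overall, for the first and second year of enrolment, on 320, 1280, 160 and 640 children-years. Each row also prints a whole number of cases.

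One exact interval is repeated in the text. "With an overall sample size of about 320 evaluable subjects by country during the first year of enrollment", and at 20 per 1000 children-years, the interval "is respectively [6.9; 40.8] for the exact Poisson distribution". On clustering the section says "we expect that the design effect will take a value of 4.18".

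SAP section 11.1.2 says that "the exact Poisson confidence limit will be used" and defines it by chi-square quantiles with 2n degrees of freedom for the lower limit and 2(n+1) for the upper, where n is the number of subjects with the event.

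**The concern.** A column labelled exact should agree with the count and the children-years in the same row. In eight rows it does not, and the disagreement always runs one way: both limits are too low and the interval is too narrow. The stated precision is therefore slightly better than the SAP's own formula would return for the same count. Section 9.3 argues from precision, so a reader may later compare reported intervals with this table. The largest discrepancies are in two country-level rows.

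**Working it through.** **Inputs.** Children-years, rates and case counts are from Table 13. The confidence level is 95%. The formula is from SAP 11.1.2, scaled to 1000 children-years (PY):

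- lower = χ²(0.025; 2n) / 2 / PY × 1000
- upper = χ²(0.975; 2(n+1)) / 2 / PY × 1000

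**Step 1: the interval in the text.** For n = 6 and PY = 320:
- 4.404/2/320 × 1000 = 6.9
- 26.119/2/320 × 1000 = 40.8

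This agrees with the protocol.

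**Step 2: all 20 rows from the printed count.** Twelve agree to the printed decimal. Eight do not. Worked example, n = 2 and PY = 160:
- 0.4844/2/160 × 1000 = 1.5
- 14.449/2/160 × 1000 = 45.2
- printed: [0.7; 40.1]

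| Cases / PY | Expected count | Printed | Exact for printed count | Upper limit too low by | Correct width larger by |
|---|---|---|---|---|---|
| 10/320 | 9.6 | [13.9; 55.4] | [15.0; 57.5] | 2.1 | 2.4% |
| 13/320 | 12.8 | [20.5; 67.5] | [21.6; 69.5] | 2.0 | 1.8% |
| 13/1280 | 12.8 | [5.1; 16.9] | [5.4; 17.4] | 0.5 | 1.4% |
| 26/1280 | 25.6 | [13.0; 29.3] | [13.3; 29.8] | 0.5 | 1.2% |
| 2/160 | 1.6 | [0.7; 40.1] | [1.5; 45.2] | 5.1 | 11% |
| 5/160 | 4.8 | [8.4; 68.5] | [10.1; 72.9] | 4.4 | 4.5% |
| 13/640 | 12.8 | [10.2; 33.7] | [10.8; 34.7] | 1.0 | 1.8% |
| 26/640 | 25.6 | [25.9; 58.6] | [26.5; 59.5] | 0.9 | 0.9% |

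At the printed upper limits the upper tail probability is 3.1% to 4.6% instead of 2.5%.

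**Step 3: the unrounded expected count** (e = rate × PY / 1000) in the same formula, without truncation. It matches none of the eight rows. For e = 1.6 it gives [0.8; 41.1], for e = 4.8 [9.5; 71.2] and for e = 9.6 [14.1; 55.8]. It also breaks rows that are now right: e = 3.2 in 320 gives [2.2; 28.3] against the printed [1.9; 27.4]. Mid-P Poisson and Clopper-Pearson limits do not reproduce the column either.

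**Step 4: the unrounded expected count with degrees of freedom cut to whole numbers**, floor(2e) and floor(2(e+1)). All 20 rows reproduce. For e = 1.6 the degrees of freedom 3.2 and 5.2 become 3 and 5:
- 0.2158/2/160 × 1000 = 0.7
- 12.833/2/160 × 1000 = 40.1

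The eight rows are exactly those in which e was rounded up to the printed count. Where e was rounded down or is whole, truncation happens to give the degrees of freedom of the printed count.

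**Step 5: the error at the nominal rate.** Against the untruncated interval of step 3, the correct width exceeds the printed width in the eight rows by at most about 2.7% (5/160: 61.7 against 60.1). For 2/160 it is 40.3 against 39.4, about 2.3%, and the upper limit is low by 41.1 − 40.1 = 1.0.

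**Step 6: the design-effect column.** Rate ± 1.96 × √(4.18 × rate / PY), with negative limits set to 0, reproduces all 20 rows.

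**The case against.** The strongest reply is that Table 13 is indexed by expected rates, so the case count is only a rounded display and the printed count is the wrong benchmark. Two cases in 160 children-years is 12.5 per 1000, not 10. The neighbouring column is computed from the rate, and the SAP formula is written for an observed n. This stands in part. Of the 5.1 points by which the 2/160 upper limit is low, about 4 come from rounding 1.6 cases to 2, and only 1.0 remains at the nominal rate. It does not rescue the column, because step 3 matches none of the eight rows.

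A second point also stands. Putting [1.5; 45.2] on a row labelled 10 per 1000, beside a design-effect interval of [0; 41.7], would leave the clustering-adjusted upper limit below the unadjusted one unless the different bases are stated.

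A reader might infer that the sample size rests wholly on a faulty column, or that reported results will be wrong. The documents do not support either reading. Table 13 also carries the design-effect intervals, which are correct and wider than the printed exact ones. The only exact interval quoted in the text is right. No formula leads from the exact limits to 2400, and the Amendment 1 rationale attributes the reduction from 3000 to complexity and budget. The analysis uses the SAP formula, not Table 13. Nor should weight be put on by-country reporting: the two clearly affected rows are country level in the second enrolment year, and no SAP incidence template is laid out by country within enrolment year.

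**Conclusion.** The point holds as a minor correction. Eight of the 20 intervals labelled exact are exact neither for the printed count nor for the unrounded expected count. Against the printed count, six rows are off by no more than about 2.4% in width, and only 2/160 (about 11%) and 5/160 (4.5%) are clearly affected. These sizes take the printed whole-number count and the SAP 11.1.2 formula as the benchmark; at the nominal rate the largest width error falls to about 2.7%. Truncated degrees of freedom as the cause is an inference from the fit to all 20 rows and is not stated in the documents. The mismatch itself does not depend on that inference.

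**What to change.** Recompute the eight rows from the printed counts with the SAP 11.1.2 formula. In table order they become [15.0; 57.5], [21.6; 69.5], [5.4; 17.4], [13.3; 29.8], [1.5; 45.2], [10.1; 72.9], [10.8; 34.7] and [26.5; 59.5]. Add a footnote that the exact column uses the rounded whole-number count (for example 2/160 = 12.5 per 1000) while the design-effect column uses the nominal rate.

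Alternatively, compute the whole exact column at the unrounded expected count without truncating the degrees of freedom, and say so. That puts both columns on one basis but changes more rows, including the interval quoted in the text: e = 6.4 in 320 children-years gives [7.6; 42.5].

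Either way, carry the corrected figures into the sample-size section of the study report. With the first option the cost is eight intervals and one footnote. Enrolment, data collection and analysis do not change.

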9. CHANGES FROM PLANNED ANALYSES

- Due to the number of subjects with examination visit but without surveillance visit:
 - RSV LRTI endpoints computed using data from examination visit were added to the endpoint RSV-associated RTI with a suspicion of involvement of the lower respiratory tract definition computed using data from surveillance visit
 - The delay between LRTI identification and swab sample is not considered in the case definition
 - The subgroup analysis by collection time of swabs (72 hours/48 hours from the start date of the case (date of the call), 72 hours/48 hours from the reported onset of symptoms) has been removed
- In protocol it is suggested to analyse by country and then pool by hemisphere and region. Pooling across such diverse settings is not developing strong messages about RSV incidence and therefore we limit our subgroup analysis to by country. Where the protocol described overall incidence we have preferred to only do pooled incidence across countries by year of life. This aids meaningful interpretation and minimises tables.
- In the analysis of the key healthcare utilization and health outcomes: the hospitalization status, intensive care unit attendance, clinical diagnosis of bronchiolitis or pneumonia, death has been replaced by: outpatient visit, emergency Room visit, inpatient Admission (non intensive care), innpatient Admission (intensive care), no consultation other than site clinic and other.
- In the analysis of the performance of case definition, the key health outcome does not include intensive care unit attendance, clinical diagnosis of bronchiolitis or pneumonia and death. Instead, hospitalization status according to WHO, GSK, Nokes, and exploratory case definition will be used for the analysis.
- The incidence rates of RSV-associated LRTI/severe LRTI as classified by the GSK and Nokes case definition are not computed.
- Incidence rate of all cause RTI provided instead of per protocol non-RSV associated RTIs as RSV RTIs are subset of all cause RTI. Hence analysis of all cause RTIs is more relevant and conventional in epidemiological studies.
- Descriptive statistics of the different types of healthcare utilization will not be provided among non-RSV-associated RTI with a suspicion of involvement of the lower respiratory tract, overall and by subgroups.

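### Protocol 9.3 implies four units in Table 13 and six in its recruitment target, while the SAP reports eight countries, so the precision stated per country cannot hold for all of them

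*Protocol*

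**What the plan says.** Three places bear on how many units the study is divided into.

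- **Protocol 9.3, text and Table 13.** The precision claim is framed per country: "With an overall sample size of about 320 evaluable subjects by country during the first year of enrollment". At 20 per 1000 the interval "is respectively [6.9; 40.8] for the exact Poisson distribution and [0; 51.7] for the normal approximation with design effect of 4.18". In the year-1 block of Table 13 the first unit-level row reads "Country/region level 320 3 10 [1.9; 27.4] [0; 32.4" and the first overall row "Overall 1280 13 10 [5.1; 16.9] [0; 21.2"; the second column is children-years. The year-2 rows are "Country/region level 160 2 10 [0.7; 40.1] [0; 41.7" and "Overall 640 6 10 [3.4; 20.4] [0; 25.8".
- **Protocol 9.3, closing paragraph.** After allowing for 20% drop-out, "approximately 400 subjects by country/region and 2400 subjects overall will need to be recruited".
- **SAP 6.3 and 9.** Section 6.3 lists eight countries: Argentina, Bangladesh, Canada, Finland, Honduras, South Africa, Thailand and the United States. Section 9 sets aside pooling by hemisphere and region: "therefore we limit our subgroup analysis to by country".

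**The concern.** Each source implies a different number of units: four, six and eight. The 320 evaluable children that Table 13 gives a unit in year 1 alone is what the recruitment target yields per unit over the whole enrollment. If country is the reporting unit, the fixed total cannot supply 320 to every country.

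Incidence is a co-primary objective and is tabulated by country. No hypothesis is tested, so the width of these intervals is the only justification offered for the sample size. A reader of the country tables would expect a precision that the design cannot provide in all eight countries.

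**Working it through.** **Inputs.** Protocol 9.3: 320 and 1280 children-years in year 1, 160 and 640 in year 2, 400 recruited per country/region, 2400 overall, 20% drop-out, intra-cluster correlation 0.02, 12 clusters of 160. Protocol 5.1: 1920 evaluable. Protocol Appendix C: 1600 recruited in year 1 and 800 in year 2. SAP 6.3: eight countries.

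**1. Reproduce the stated interval (20 per 1000, 320 children-years).**
- Design effect: 1 + (160 − 1) × 0.02 = 4.18.
- Normal limits: 20 ± 1.96 × √(4.18 × 0.020 / 320) × 1000 = 20 ± 31.7, floored at zero: [0; 51.7].
- Exact Poisson limits: χ²(0.025; 2n)/(2 × PY) and χ²(0.975; 2n + 2)/(2 × PY), where PY is children-years. With n = 0.020 × 320 = 6.4, the degrees of freedom 12.8 and 14.8 truncate to 12 and 14: [6.9; 40.8].

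With this convention all 20 rows of Table 13 reproduce to one decimal. Using the printed, rounded case counts misses some rows (10 cases in 320 gives [15.0; 57.5], not [13.9; 55.4]). That is a rounding matter only.

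**2. Count the units.**
- Table 13: 1280/320 = 4 and 640/160 = 4. Each unit has 320 + 160 = 480 evaluable, hence 480/0.8 = 600 recruited.
- Recruitment target: 2400/400 = 6. Each unit has 400 × 0.8 = 320 evaluable over the whole enrollment.
- SAP: 8.

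**3. How many countries can reach 320, under any allocation?**
- Year 1: 1280/320 = 4.
- Both years: 1920/320 = 6.
- With no drop-out at all: 1600/320 = 5 in year 1, and 2400/320 = 7.5, so seven, over both years.
- All eight at 320 in year 1 would need 8 × 320 = 2560 evaluable, or 2560/0.8 = 3200 recruited. The plan recruits 1600.

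**4. Illustrative intervals at 20 per 1000.** These assume an equal split, which the documents do not give, and keep the design effect at 4.18. Ratios are to the stated exact width (33.9) and design-effect half-width (31.7).

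| Units, years | Children-years | Exact | Ratio | With design effect | Ratio |
|---|---|---|---|---|---|
| As stated | 320 | [6.9; 40.8] | 1 | [0; 51.7] | 1 |
| Six, year 1 | 213 | [5.1; 48.0] | 42.9/33.9 = 1.27 | [0; 58.8] | 38.8/31.7 = 1.22 |
| Six, both | 320 | [6.9; 40.8] | 1 | [0; 51.7] | 1 |
| Eight, year 1 | 160 | [3.9; 54.8] | 50.9/33.9 = 1.50 | [0; 64.8] | 44.8/31.7 = 1.41 |
| Eight, both | 240 | [5.6; 45.7] | 40.1/33.9 = 1.18 | [0; 56.6] | 36.6/31.7 = 1.15 |

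**5. Which row matches the planned analysis?** The SAP incidence templates (12.3.1) are by country and age interval, not by enrollment year, so the last row applies. It is somewhat pessimistic. Protocol 8.2 keeps data up to withdrawal, and SAP 11.1.1 counts person-time to last contact. First-year child-years therefore lie between about 1920 and 2400, or 240 to 300 per country. At 300 (6 cases) the exact interval is [7.3; 43.5], which is 36.2/33.9 = 1.07 times as wide.

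**6. Overall rows.** 1600 × 0.8 = 1280 and 800 × 0.8 = 640, as printed.

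**The case against.** The best defence is that Table 13 describes regions. Its rows are labelled country/region, and Appendix C controls recruitment by country so as to secure an adequate regional population. Four regions fit the table exactly, and 4 × 400 = 1600 matches year-1 recruitment. The eight countries and the country-only rule come from the later SAP, which declares the change openly. All analyses are descriptive, and each country estimate will carry its own exact interval.

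Some of this stands. A reader might infer that Table 13 is miscalculated. It is not: every row reproduces, and the fault lies in the denominator credited to a country. A reader might also infer that reported country intervals will be 1.5 times as wide as planned. That ratio belongs to enrollment year 1 alone, which the SAP incidence tables do not report separately. With both years combined, the six-unit reading gives exactly the printed precision. RSV-associated LRTI is expected at eight times the hospitalization rate, so its relative precision is better than these rows show.

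The regional reading still does not remove the problem. The sentence in 9.3 says by country. The closing paragraph sets 400 beside 2400, not 1600, with no year-1 qualifier. The SAP has dropped regional pooling, so a region-level precision would describe no planned subgroup analysis.

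**Conclusion.** The inconsistency is real. Protocol 9.3 and the SAP together use four, six and eight units, and the precision stated for 320 evaluable children by country cannot hold in all eight: at most four reach 320 in year 1 and at most six over both years. That conclusion needs only the plan's totals and its 20% drop-out, not an equal split.

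The shortfall is modest for the analysis actually planned. With equal allocation and both enrollment years combined, intervals are about 1.15 to 1.2 times as wide as stated, and less if the person-time of drop-outs is counted. Overall precision is unaffected, and no power claim is involved. A correction should be made, but it does not threaten the study's conclusions.

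**What to change.** - State once, in Protocol 9.3, how many countries and how many regions the study has, and reconcile 320 of 1280 with 400 of 2400.
- Restate the country-level rows of Table 13 and the sentence above it from the actual country allocation, with both enrollment years pooled as the SAP analyses them. Show equal-split figures (240 per country) only as a labelled illustration. Year-specific values of 160 and 80 should not simply be substituted, because the documents give no country targets.
- If the present rows are kept, label them as four pooled regions rather than countries, and correct the closing paragraph of 9.3 to match.

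The cost is a text correction and less favourable planning figures at country level. No extra subjects are needed.
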